8.1.3 Comparison of FET PET to Standard of Truth

The results of the FET PET scan will be compared to a standard of truth (either CSOT or histopathology standard of truth, as described above).

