8.1.3.1 Lesion-level Analyses

For lesion-specific analyses, lesions will be classified as either TP, FP, TN, or FN:

- True positive (TP): FET PET read as positive for progression/recurrence, standard of truth confirms tumor progression/recurrence.
- False positive (FP): FET PET read as positive for progression/recurrence, standard of truth does not confirm progression/recurrence.
- True negative (TN): FET PET read as negative for progression/recurrence, standard of truth confirms negative for progression/recurrence.

- False negative (FN): FET PET read as negative for progression/recurrence, standard of truth does not confirm progression/recurrence.
- For any lesion that is recorded by only one of the expected evaluations (either by a blinded reader or by the standard of truth) after receiving both evaluations, the non-recorded evaluation will be assessed as negative for determination of the lesion-specific result (TP, FP, TN, or FN).

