8.1.3.2 Subject-level Analyses

Subject-level results will be determined for each reader based on the lesion-level result(s):

- First, each lesion will be determined as TP, TN, FP, or FN by comparing the FET PET determination to the standard of truth.
- If the subject has only one lesion, then the subject-level result (for that reader) will be the same as the lesion-level determination.
- If the subject has two or more lesions, then the subject-level result (for that reader) will be a lesion-level result according to the following hierarchy, based on the potential clinical impact of these reads.
 - TP > FP > FN > TN > Missing
 - For example, if a subject has one TP lesion and one FN lesion (according to a specific reader), then the subject-level result (according to that reader) will be TP.

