9.2.3 Analysis of Secondary Endpoints

For the secondary endpoints for performance characteristics, both the composite reference standard and histopathology alone will be used in separate calculations. Only the efficacy analysis set will be analyzed for secondary efficacy endpoints; the per protocol population will not be analyzed. TP, FP, FN, and TN are defined as described in [Section 8.1.3](#).

Calculations will be done to determine the subject-specific and lesion-specific sensitivity, specificity, positive predictive value, negative predictive value, accuracy, and misclassification rate for FET PET. These analyses will use the blinded readers' overall assessment, not the visual/qualitative or quantitative assessments.

For the secondary analyses of sensitivity, specificity, PPV, NPV, accuracy, and misclassification rate that use histopathology as the standard of truth, analysis will be performed only on subjects who have known histopathology status. No imputation will be made for these endpoints.

Inter-reader variability will be analyzed using Fleiss' kappa statistic to determine the agreement between three independent blinded readers in assessing FET PET images as recurrence or TRC. Separate analyses of inter-reader variability will be done for the readers' qualitative/visual assessments, quantitative assessments, and overall assessments.

Intra-reader variability will be analyzed based on a random sample of 15 subjects whose images were re-reviewed by the same reader. The percent of agreement between the two interpretations will be computed for each reader. Cohen's kappa statistics will be used to determine the reproducibility of the assessment by individual readers when analyzing the same data repeatedly. Separate analyses of intra-reader variability will be done for the reader's qualitative/visual assessments, quantitative assessments, and overall assessments.

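### The rule that scores a non-recorded evaluation as negative is not limited to the composite standard; on its more natural reading it makes un-sampled lesions truth-negative in the histopathology analyses, against the no-imputation statement.

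*Combined protocol and SAP*

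**What the plan says.** Section 8.1.3 has FET PET "compared to a standard of truth (either CSOT or histopathology standard of truth, as described above", so one set of TP, FP, TN and FN definitions serves both standards.

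The last bullet of Section 8.1.3.1 adds a rule for lesions that appear on one side only. Its scope is "For any lesion that is recorded by only one of the expected evaluations (either by a blinded reader or by the standard of truth". Its condition is that both evaluations have been received, and its effect is that "the non-recorded evaluation will be assessed as negative for determination of the lesion-specific result". Nothing limits it to the CSOT.

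Section 8.1.3.2 builds the subject-level result from the lesion results by the order "TP > FP > FN > TN > Missing".

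Section 9.2.3 takes the four definitions from Section 8.1.3 for all secondary performance measures. For the histopathology versions it keeps only subjects whose histopathology status is known, and then says "No imputation will be made for these endpoints". Section 2.2 lists these measures at both subject and lesion level. No passage says what happens to an un-sampled lesion in a subject who has tissue from a different lesion.

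**The concern.** A lesion from which no tissue was taken is not thereby shown to be tumour-free. If the rule reaches such lesions, lesion-level specificity, PPV and accuracy against histopathology depend partly on which lesions happened to be biopsied. The subject-level results move as well, because FP outranks FN and TN.

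The situation is one the plan foresees. Section 8.1.2.1 describes a distinct lesion being sampled while the lesion of concern was not. Section 5.2.1.1 lets FET findings inform biopsy and surgery, and plans one to four targeted samples where possible. Whether a lesion has tissue may therefore depend on the test under study.

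Agreement with histopathology is the first secondary objective, and Section 1.1 says that the data are meant to support a marketing application.

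**Working it through.** **Step 1: which lesions the rule reaches.** Take a subject with two FET-read lesions and tissue from one. The Section 9.2.3 filter keeps the subject, because histopathology status is known. It does not remove the second lesion.

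- If the condition in "after receiving both evaluations, the non-recorded evaluation will be assessed as negative" refers to the subject, it is met. The second lesion is recorded by the reader only, so its truth is set to negative. This contradicts "No imputation will be made for these endpoints".
- If it refers to the lesion, the second lesion never received a histopathology evaluation. The rule does not apply and there is no conflict.

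The subject reading is the more natural one: a lesion that had itself received both evaluations would normally have both recorded, leaving the rule little to do.

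**Step 2: lesion-level size.** The plan gives no figure for this, so there is nothing to reproduce. Inputs from Section 9.1.1: sensitivity 0.81, specificity 0.79, prevalence 0.50. Assumptions: 100 sampled lesions, *u* un-sampled lesions added, and the same prevalence and FET performance in both. FN is taken as FET-negative and truth-positive, as the sensitivity formula in Section 8.2.2 requires.

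Sampled lesions: TP = 40.5, FN = 9.5, TN = 39.5, FP = 10.5. The share of un-sampled lesions read FET-positive is 0.5 × 0.81 + 0.5 × 0.21 = 0.51.

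- Specificity = (39.5 + 0.49*u*) / (50 + *u*)
- PPV = 40.5 / (51 + 0.51*u*)
- Accuracy = (80 + 0.49*u*) / (100 + *u*)

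| *u* | Specificity | PPV | Accuracy |
|---|---|---|---|
| 0 | 39.5/50 = 0.79 | 40.5/51 = 0.794 | 80/100 = 0.80 |
| 10 | 44.4/60 = 0.74 | 40.5/56.1 = 0.722 | 84.9/110 = 0.77 |
| 30 | 54.2/80 = 0.68 | 40.5/66.3 = 0.611 | 94.7/130 = 0.73 |

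Lesion-level sensitivity stays at 0.81, because no un-sampled lesion enters its denominator.

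**Step 3: how far the assumptions matter.** Specificity depends on recurrence among the un-sampled lesions. At *u* = 30, if none are recurrent it stays at (39.5 + 30 × 0.79)/80 = 0.79. If all are recurrent it is (39.5 + 30 × 0.19)/80 = 0.565.

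With prevalence 0.70 throughout (the high-grade figure in the superseded calculation of Section 9.1.2), the FET-positive share is 0.7 × 0.81 + 0.3 × 0.21 = 0.63. Specificity is then (23.7 + 3.7)/40 = 0.685 at *u* = 10 and (23.7 + 11.1)/60 = 0.58 at *u* = 30. At *u* = 30, PPV falls from 56.7/63 = 0.90 to 56.7/81.9 = 0.69.

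**Step 4: subject level.** Let *q* be the share of subjects who also have an un-sampled FET-positive lesion, assumed independent of the sampled lesion's result. By the hierarchy, TN and FN subjects become FP, while TP and FP subjects stay. An un-sampled FET-negative lesion, scored TN, changes no subject result.

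- Sensitivity = 40.5 / [40.5 + 9.5(1 − *q*)]
- Specificity = 39.5(1 − *q*) / [39.5(1 − *q*) + 10.5 + 49*q*]

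| *q* | Sensitivity | Specificity |
|---|---|---|
| 0 | 0.81 | 0.79 |
| 0.05 | 0.818 | 0.743 |
| 0.10 | 40.5/49.05 = 0.826 | 35.55/50.95 = 0.698 |
| 0.30 | 40.5/47.15 = 0.859 | 27.65/52.85 = 0.523 |

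Since *q* counts FET-positive lesions only, 10% of subjects with one extra lesion of either read corresponds to *q* of about 0.05. Sensitivity rises only because histology-proven missed tumours leave its denominator and are counted as truth-negative.

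**The case against.** The strongest reply is that the rule never reaches un-sampled lesions. Grammatically its condition qualifies the lesion. Section 6.1.2 does not require biopsy, so no histopathology evaluation was expected for such a lesion. Section 8.1.2.2 sets a histopathology standard only where tissue exists. The Missing level in the hierarchy would have little use if every absent evaluation became negative. And the no-imputation sentence, being specific to these endpoints, can be read as overriding the general rule.

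This stands as a possible reading. A reader might infer that the two sections flatly contradict each other, but the documents do not support that much: the contradiction holds only if the condition refers to the subject. The lesion reading still leaves a gap, however. FP is defined as "FET PET read as positive for progression/recurrence, standard of truth does not confirm progression/recurrence", whereas TN needs positive confirmation of absence. A FET-positive lesion without tissue fits the FP wording even without the last bullet. Two programmers following this text could produce different tables.

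It is also fair to say that the size is hypothetical. The documents do not say how often glioma subjects have more than one lesion, so the effect could be close to nil. Finally, removing un-sampled lesions does not remove the selection in which lesions get biopsied.

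**Conclusion.** The point holds as an ambiguity whose more natural reading contradicts Section 9.2.3 and misclassifies lesions and subjects. The illustrative fall in lesion-level specificity, from 0.79 to about 0.74 or 0.68, rests on an assumed 10% or 30% of extra un-sampled lesions and on equal prevalence in sampled and un-sampled lesions. It measures sensitivity to the rule and does not predict what the trial will show.

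A reader might also infer that the study's success criterion is at risk. It is not. The primary endpoints use the CSOT, which Section 8.1.2.1 sets for each individual lesion, and the criterion in Section 9.2.2 does not use the histopathology standard of truth. Subjects with no histopathology at all are excluded from these endpoints on either reading. A change is still warranted, because a stated rule can yield wrong specificity, PPV and subject-level results for the first secondary objective.

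**What to change.** State in Section 8.1.3.1 that the non-recorded-as-negative rule applies to CSOT comparisons only. It still has a purpose there: the Truth Panel works independently of the FET images, so its lesion list and a reader's can differ.

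For the histopathology standard, state that a lesion without a specimen is Missing, is excluded from lesion-level counts, and does not determine the subject-level result. This uses the Missing level already in Section 8.1.3.2, settles both readings and the FP wording, and agrees with Section 9.2.3.

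The cost is a short addition to the text, one programming condition, and slightly fewer lesions in the histopathology tables. The report should acknowledge that these tables still describe only lesions selected for tissue sampling, a selection that FET findings may have influenced.

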2.2 Secondary Objectives

| Secondary Objectives | Endpoints | Time Frame |
|--|---|-----------------|
| 1. To determine if FET PET can differentiate between benign TRC and recurrent glioma in comparison to a histopathological standard of truth. | 
 • Sensitivity of FET PET using a histopathology standard of truth (subject- and lesion-level) • Specificity of FET PET using a histopathology standard of truth (subject and lesion-level) • Positive Predictive Value (PPV) of FET PET using a histopathology standard of truth (subject and lesion-level) • Negative Predictive Value (NPV) of FET PET using a histopathology standard of truth (subject and lesion-level) • Accuracy of FET PET using a histopathology standard of truth (subject and lesion-level) • Misclassification Rate of FET PET using a histopathology standard of truth (subject and lesion-level) | Up to 6 months. |
| 2. To determine if FET PET can differentiate between benign TRC and recurrent glioma in comparison to a CSOT evaluated using estimates other than subject-based sensitivity and specificity. | 
 • Sensitivity of FET PET using a CSOT (lesion-level) • Specificity of FET PET using a CSOT (lesion-level) • PPV of FET PET using a CSOT (subject and lesion-level) • NPV of FET PET using a CSOT (subject and lesion-level) • Accuracy of FET PET using a CSOT (subject and lesion-level) • Misclassification Rate of FET PET using a CSOT (subject and lesion-level) | Up to 6 months. |

| Secondary Objectives | Endpoints | Time Frame |
|---|--|-----------------|
| 3. To assess the safety of FET PET, as determined by treatment emergent adverse events (TEAEs) within 48 hours of FET administration. | Incidence of treatment-emergent adverse events (TEAEs) | Up to 48 hours. |
| 4. To describe the inter-reader variability between 3 independent blinded readers of FET PET images in their assessments of benign TRC versus recurrent glioma. | Fleiss' kappa | N/A |
| 5. To describe intra-reader variability between 3 independent blinded readers of FET PET images in their assessments of benign TRC versus recurrent glioma. | Cohen's kappa | N/A |

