8.1 Determination of Positive or Negative Disease Status

8.1.1 FET PET Blinded Reads

All imaging studies will be reviewed by three nuclear medicine physicians blinded to the patient's history and their pathology. Each physician will undergo a reader-training course that will involve FET PET cases not included in the study reads. Image interpretation will involve 1) qualitative, 2) quantitative, and 3) overall assessments.

1) Qualitative/Visual Assessment

For each lesion, readers will assess whether increased tracer uptake is consistent with progression/recurrence (positive) or TRC (negative).

2) Quantitative Assessment

Quantitative assessments will be performed on transaxial slices showing the highest FET accumulation, as described by Galldiks (6). The SUVmax, TBRmax and TBRmean and size information will be collected. Based on the quantitative assessments, readers will evaluate in a binary fashion for progression/recurrence (positive) or TRC (negative) as defined in Galldiks (6) (TBRmax ≥ 2.3 and/or TBRmean ≥ 2.0 for use in indeterminate cases).

3) Overall Assessment

Based on qualitative and quantitative assessments, readers will make an overall determination whether FET uptake is most consistent with progression/recurrence (positive) or TRC (negative). In cases where readers disagree with the quantitative assessment, based on their expert judgement, they will be prompted to provide comments. The overall assessment will be the positive or negative determination for FET PET.

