8.1.2 Standard of Truth

8.1.2.1 Composite Standard of Truth

A composite standard of truth (CSOT) for recurrence or TRC will be evaluated by a panel of physicians (Truth Panel) independent of the FET images, FET imaging reports, or FET blinded reads. The CSOT will be determined based on histopathology reports and other available clinical information, including prior imaging, subsequent imaging, tumor board notes, clinical notes. Histopathology of the target lesion obtained (biopsy, resection) within three months after the PET imaging session will be reviewed (although the Truth Panel will have access for up to six months after the PET imaging session). There is no agreed upon cutoff for determining recurrent tumor in the setting of gliomas. A 20% cutoff is often used, but a truth panel will include a pathologist for manual re-review of histopathology. Positive for recurrence on follow-up imaging will be based on RANO 2.0 criteria (4).

For lesion-level reference standard, features of RANO will be leveraged as part of the overall assessment and will be considered in evaluating lesion-level results. Histopathology and imaging will be the primary factors used in the determination, followed by additional clinical data available as part of tumor board notes. From this data, an overall determination will be made for each individual lesion, and this will be considered together with the patient-level determination (as per RANO).

In patients where the histopathology and RANO determination are concordant, the patient will be characterized based on the concordant results. If the patient does not have subsequent imaging available (either the patient declined clinically or the lesion was resected and so not present on subsequent imaging), the patient will be characterized based on histopathology for lesions resected or as progressive disease if there is clinical decline or death.

There will be many complicating factors for the CSOT:

1. The use of steroids and bevacizumab can impact lesion enhancement independent of actual progression. For example, a lesion may have decreased enhancement after a patient starts bevacizumab, but in fact have progressive disease (pseudo- response). In this case the RANO determination would be PR, while the patient could be characterized as recurrent disease by the Truth Panel. In order to take this into consideration, the Truth Panel will look at subsequent imaging studies to determine the appropriate characterization.

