8.2.2 Efficacy Variables

The sensitivity and specificity of FET PET imaging will be calculated according to the above formula along with Wilson's binomial (score) 95% confidence intervals.

- **Sensitivity**

Sensitivity is defined as the proportion of study patients with a true positive (TP) FET PET scan relative to those with positive standard of truth result:

$$\text{Sensitivity (\%)} = [\text{TP} / (\text{TP} + \text{FN})] \times 100$$

- **Specificity**

Specificity is defined as the proportion of study patients with a true negative (TN) FET PET imaging result relative to those with a negative standard of truth result:

$$\text{Specificity (\%)} = [\text{TN} / (\text{TN} + \text{FP})] \times 100$$

The positive predictive value, the negative predictive value, accuracy, misclassification rate, standardized uptake value, and tumor-to-background ratio will be calculated as follows:

- **Positive predictive value (PPV)**

The positive predictive value is defined as the probability that a positive standard of truth result is obtained given that the result of the FET PET scan is positive.

$$\text{PPV (\%)} = [\text{TP} / (\text{TP} + \text{FP})] \times 100$$

- **Negative predictive value (NPV)**

The negative predictive value is defined as the probability that a negative standard of truth result is obtained given that the result of the FET PET scan is negative.

$$\text{NPV (\%)} = [\text{TN} / (\text{TN} + \text{FN})] \times 100$$

- **Accuracy**

The accuracy is defined as the probability that the FET PET scan result is correct.

$$\text{Accuracy (\%)} = [(\text{TP} + \text{TN}) / (\text{TP} + \text{FP} + \text{TN} + \text{FN})] \times 100$$

- **Misclassification Rate**

The misclassification rate is defined as the probability that the FET PET scan result is not correct.

$$\text{Misclassification Rate (\%)} = [(\text{FP} + \text{FN}) / (\text{TP} + \text{FP} + \text{TN} + \text{FN})] \times 100$$

- **Standardized Uptake Value (SUV) and Tumor-to-Background Ratio (TBR)**

Quantitative assessments will be performed on transaxial slices showing the highest FET accumulation. Quantitative analysis will be performed on the 20-40 minute imaging time point.

First, readers will determine the SUVmean of background normal tissue by marking a large region of interest (ROI) on the contralateral hemisphere in an area of unaffected brain tissue.

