Second, a volume of interest will be placed around the lesion, and within that volume a threshold segmentation will be performed using a lower limit threshold of background SUVmean x 1.6.

Third, a 1.6 cm diameter circular ROI will be centered on the qualitatively hottest portion of FET uptake. TBRmax will be calculated by dividing the SUVmean of the 1.6 cm diameter circular ROI by the SUVmean of background normal tissue. TBRmean will be calculated by dividing the SUVmean of the lesion volume of interest (using the background SUVmean x 1.6 threshold) by the SUVmean of background normal tissue. Lesions will be quantitatively evaluated in a binary fashion as recurrence if TBRmax >

2.3 or treatment-related changes if TBRmax < 2.3. For indeterminate lesions, readers can use TBRmean to evaluate for recurrence vs. treatment-related changes.

Additionally, the SUVmax of the lesion and the SUVpeak will also be calculated.

9 Statistical Considerations and Evaluation of Results

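### A site that only a reader records, and reads as negative, is counted as a lesion-level true negative with no site-specific truth assessment, so CSOT lesion-level specificity, NPV and accuracy depend partly on how many such sites each reader marks

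*Combined protocol and SAP*

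**What the plan says.** Section 8.1.3.1 classifies each lesion as TP, FP, TN or FN by setting the reader's call against the standard of truth. A TN needs a negative read and a truth result for which the "standard of truth confirms negative for progression/recurrence". The last bullet of the section covers lesions that only one side recorded, once both the read and the truth evaluation are in for the patient: "the non-recorded evaluation will be assessed as negative for determination of the lesion-specific result".

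Four other places bear on how that rule works:

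- Section 8.1.1 asks three blinded readers for a positive or negative call on each lesion. It gives no common lesion list, minimum size or limit per patient.
- Section 8.2.2 makes the quantitative call on a low-uptake site negative: "treatment-related changes if TBRmax < 2.3".
- Section 8.1.2.1 has the Truth Panel work "independent of the FET images, FET imaging reports, or FET blinded reads".
- Section 8.2.2 defines specificity as true negatives "relative to those with a negative standard of truth result", so every TN enters both numerator and denominator.

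Section 2.2, objective 2, names lesion-level specificity, NPV, accuracy and misclassification rate against the CSOT as secondary endpoints.

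**The concern.** The panel does not see the FET images or reads, so it cannot know that a reader has marked a given site. If the panel has not listed that site and the reader calls it negative, the rule supplies a negative truth value and the pair is scored as a correct read. That does not fit the TN definition a few lines above it, which requires the truth standard to confirm the negative.

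The count of such sites is not bounded by anything in the plan and is set by each reader separately. One reader may record every faint focus and another only the dominant lesion. Their lesion-level specificity, NPV and accuracy would then differ even if they agreed on every lesion that the panel listed, and the reader who marks more would also have narrower intervals. At stake is whether these secondary results can be read as diagnostic performance and compared across the three readers.

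**Working it through.** **No figure to reproduce.** The plan gives no lesion count, lesion-level sample size or lesion-level threshold. The rule is therefore traced case by case, and its size is shown on assumed tables.

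**Step 1: the rule applied to one-sided lesions.**

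| Recorded by | Call | Value supplied for the other side | Result |
|---|---|---|---|
| Reader only | positive | truth negative | FP |
| Reader only | negative | truth negative | TN |
| Panel only | positive | read negative | FN |
| Panel only | negative | read negative | TN |

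FN is taken here as a negative read with positive truth, as the sensitivity formula in section 8.2.2 requires. The printed FN definition in 8.1.3.1 is worded differently.

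**Step 2: what marking a negative site does.**

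- Panel lists the site as positive: FN, whether or not the reader marked it.
- Panel lists it as negative: TN, whether or not the reader marked it.
- Panel does not list it: one TN if marked, nothing if not.

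So recording a negative site never costs the reader anything and sometimes adds a TN.

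**Step 3: formulas with k reader-only negative sites added.**

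- Specificity = (TN + k) / (TN + k + FP), which rises if FP > 0.
- NPV = (TN + k) / (TN + k + FN), which rises if FN > 0.
- Accuracy = (TP + TN + k) / (TP + FP + TN + FN + k), which rises if there is any error.
- Sensitivity and PPV contain no TN and do not move.

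**Step 4: illustration A.** Assumption: the subject-level planning values in section 9.1.1 (N = 118, prevalence 0.50, sensitivity 0.81, specificity 0.79) are applied to lesions, one per patient. Then 118 × 0.50 = 59 positive and 59 negative; 0.81 × 59 ≈ 48 TP, leaving 11 FN; 0.79 × 59 ≈ 47 TN, leaving 12 FP. The values k = 12, 30 and 59 correspond to about 0.1, 0.25 and 0.5 sites per patient in 118 patients. These rates are also assumptions.

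| k | Specificity (Wilson 95% CI) | NPV | Accuracy |
|---|---|---|---|
| 0 | 47/59 = 79.7% (67.7 to 88.0) | 47/58 = 81.0% | 95/118 = 80.5% |
| 12 | 59/71 = 83.1% (72.7 to 90.1) | 59/70 = 84.3% | 107/130 = 82.3% |
| 30 | 77/89 = 86.5% (77.9 to 92.1) | 77/88 = 87.5% | 125/148 = 84.5% |
| 59 | 106/118 = 89.8% (83.1 to 94.1) | 106/117 = 90.6% | 154/177 = 87.0% |

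**Step 5: illustration B, a lower assumed base of 42/60.** Specificity goes from 70.0% (57.5 to 80.1) to 54/72 = 75.0% (63.9 to 83.6), 72/90 = 80.0% (70.6 to 87.0) and 101/119 = 84.9% (77.4 to 90.2) for the same k.

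**Step 6: reader-only positives.** With m such sites added as FP, specificity is (47 + k) / (59 + k + m) in illustration A. This exceeds 47/59 only if k/(k + m) > 47/59, that is, if more than about 80% of reader-only sites are read negative. With k = m = 12 it is 59/83 = 71.1%, below the base. NPV contains no FP, so reader-only positives do not offset the rise there.

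**Step 7: subject level.** Section 8.1.3.2 ranks TN below TP, FP and FN and above only Missing. An extra TN can change a patient's result only from Missing to TN.

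**The case against.** The strongest reply has four parts.

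- **The sites may be few.** Readers are trained and are asked about lesions, not physiologic uptake. Population 1 enters with suspected recurrence on MRI, and section 8.1.2.1 describes the aim as characterizing lesions already present at the FET PET. The panel sees prior and later imaging and can list what is visible there. This stands: the documents give no frequency, and the top case above needs one unlisted negative site in every second patient.
- **The truth side is not blank.** The rule applies only after the panel has evaluated the patient, so listing nothing at a site is weak evidence that nothing was there. This also stands. What is missing is an assessment of that site, not any review at all.
- **The rule cuts both ways.** It makes every reader-only positive an FP without site-specific truth. Step 6 confirms that the net effect on specificity can be downward.
- **The consequence is limited.** Study success in section 9.2.2 rests on subject-level sensitivity and specificity, and no lesion-level threshold is set. For the histopathology endpoints, section 9.2.3 rules out imputation, which may switch the rule off there.

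A reader might infer that the rule favours FET overall, or that readers could inflate their results on purpose. The documents support neither. The net direction depends on an unknown mix, and nothing suggests intent; ordinary differences in marking habits are enough. A reader might also infer that the primary endpoints are biased, which Step 7 does not bear out.

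None of this removes the narrower point: an unassessed site is scored as a confirmed negative, and the number of such sites varies by reader.

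**Conclusion.** The point holds for the CSOT lesion-level secondary endpoints. A reader-only negative site becomes a TN that does not meet the plan's own TN definition. Each one moves specificity, NPV and accuracy up or leaves them where they are, moves the misclassification rate the opposite way, and makes denominators reader-specific. On the assumed tables, 12 to 59 such sites add about 3 to 10 percentage points to specificity from a base of 79.7%, and 5 to 15 points from a base of 70%. The lesion counts, base rates and site frequencies are all assumptions; only the direction of each single site's effect follows from the text. Whether the rule reaches the histopathology lesion-level endpoints is unclear, and sections 8.1.3.1 and 9.2.3 should be reconciled on that. The weight is that of a change that should be made, not one on which the primary result depends.

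**What to change.** In section 8.1.3.1:

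1. Calculate the CSOT lesion-level measures on the lesions recorded by the Truth Panel, which are the same for all three readers. Keep the rule that a panel-listed lesion not recorded by a reader counts as FET-negative.
2. Do not count reader-only sites read negative as TN. List them by reader.
3. Report reader-only sites read positive as a count per reader, with a second table that adds them as FP, as the current rule does. This keeps their unfavourable effect visible without making the main denominators differ by reader.
4. State that the change concerns the lesion-level measures only, so that the subject-level results built up in section 8.1.3.2 are not altered by accident.

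The cost is a short text change and one extra table per lesion-level analysis. No new data, patients or reads are needed. Compared with counting reader-only negatives as TN, lesion-level specificity, NPV and accuracy may come out slightly lower.
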